12.3 Justification of Sample Size

PROTOCOL TITLE: Ketamine for the Treatment of Opioid Use and Depression Version Date: December 20, 2021

For a 75% anticipated enrollment rate from the initial prescreened sample of 40 individuals, feasibility can be estimated within a margin of error of 14% with 95% confidence. Similarly, assuming a 60% rate of study enrollment of eligible participants, with a sample size of 30 we can estimate feasibility within a 17% margin of error with a 95% confidence interval. This study is powered to estimate the effects of ketamine on significant reduction in MADRS symptoms at the end of one month (see Hypothesis 1). Over the course of a two-year study, we estimate that we will be able to recruit 15 patients in each of the two intervention arms (2/month over 15 months). At 80% power, this sample size will allow us to detect a minimum difference in MADRS scores of 14.4 at one month between the ketamine and the placebo groups in a study design with 7 repeated measurements having a AR(1) correlation of 0.9, and a standard deviation of 15.8, with a significance level of 0.050 (Singh et al., 2016; Niciu et al., 2014). While we will examine changes in depression severity as a continuous variable, we will also examine other clinically accepted changes in depression severity such as response (defined as a 50% reduction in symptom severity from baseline) and remission (defined as below the threshold for mild depression which is a score of 6 on the MADRS). Baseline averages for the MADRS scores for this population will be assumed to be 34 (Niciu et al., 2014; Han et al., 2016; Singh et al., 2016). The minimum difference in MADRS of 14.4 is anticipated to be approximately 50% of the baseline measurements. Although there is limited information on the effectiveness of ketamine in the treatment of addiction, a sample of 30 subjects (15 in each arm) will provide adequate power to detect an 22% difference between the two groups in the percent of days abstinent from opioid use using the same longitudinal design as described above with 7 time points (Hypothesis 2). For this calculation, we assumed an AR(1) correlation of 0.9 and a standard deviation of 25% at a significance level of 0.05; an arcsine transformation was used for variance stabilization. Over the 8-week follow-up period, we will examine if there exists a threshold point in time where the effect of ketamine plateaus. To achieve this, we will use a segmented regression analysis using non-linear mixed models. We will take all efforts to keep dropouts to a minimum. However, our past experience suggests the rates of dropout are up to 20%. This could reduce the sample size per group to 12 and 12. The corresponding differences we could detect would be a minimum MADRS score difference of 16.1 and a 26% difference between groups in terms of the percent of days abstinent from opioid use. No interim analyses are planned.

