4.2 Secondary Outcomes

Secondary outcomes will include changes in depression severity (as measured on the Montgomery– Asberg Depression Rating Scale), which will be calculated as a change from baseline to 4-week followup.

Montgomery Asberg Depression Rating Scale (MADRS; Montgomery, 1979). The MADRS is a clinician administered, 10-item questionnaire of depression severity. The total score ranges from 0-60, with scores of 0-6 considered normal (non-depressed), 7-19 indicative of mild depression, 20-34 indicative of moderate depression, and 35-60 indicative of severe depression. Individuals scoring 20 or higher on the MADRS will be included in the study. The MADRS evaluates the following symptoms of depression: 1) clinical appearance of sadness, 2) self-reported sadness, 3) inner tension, 4) reduced sleep, 5) reduced appetite, 6) concentration difficulties, 7) lassitude, 8) inability to feel, 9) pessimistic thought process, and 10) thoughts of suicide. The MADRS has a sensitivity of 94% and a specificity of 83%, has been shown to have high internal consistency, and correlates well with other measures of depression such as the Hamilton Depression Scale.

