12.0 DATA MANAGEMENT

12.1 Data Analysis Plan

Baseline demographic characteristics will be collected and descriptive statistics will be used to characterize participants. Data will be collected and managed using the secure REDCap (Research Electronic Data Capture) database. Descriptive statistics for primary outcomes will include 1) the percentage of individuals completing informed consent out of the number of individuals eligible on the

initial screening and 2) the percentage of individuals that complete informed consent which complete the full protocol. Other descriptive statistics for the sample population will be analyzed, and baseline characteristics that are found to be significantly associated with other outcome measures will be included as covariates. Spaghetti plots will be produced to guide modeling outcomes as a function of time. All analyses will be conducted based on intention to treat. Subjects assigned to Group B (placebo) who complete Study Wk4 (at which time main outcomes are assessed), may choose to receive 8 ketamine treatments before completing follow-up visits. To preserve study blinding, subjects who are among the final 6 subjects being enrolled will not be unblinded until primary outcomes are assessed for all 30 subjects.

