12.2 Hypotheses for Analyses

Feasibility Hypothesis: From the cohort of individuals completing the initial prescreening assessment, a 75% study enrollment rate will be deemed feasible. Therefore, we anticipate that 40 individuals will be needed to complete prescreening so that 30 participants will enroll in the study. Of the individuals enrolling in the study, we anticipate 60% of participants will *complete* the study protocol. *Completion* is defined for the study purposes as completing at least 75% of the study visits.

Hypothesis 1: Ketamine will result in significantly greater reduction in depression symptoms as compared to placebo at one-month. To test this hypothesis, we will employ repeated measures ANOVA using linear mixed models approach to assess reduction on the total score of the MADRS.

Hypothesis 2: Ketamine will result in significantly greater reduction in frequency of opioid use as compared to placebo at one-month. To test this hypothesis, we will treat the percent days using opioids (TLFB) as a continuous variable and analyze using linear mixed models approach. Abstinence at one-week (on UDS) will be compared by intervention groups using logistical regression analyses. An arcsine square root or logit transformation may be considered to stabilize variance of the proportions.

Hypothesis 3: Response to ketamine will be influenced by changes in motivation to quit (URICA) and qualities of psychoactive perceptual experience (HMS). To test this hypothesis, we will employ repeated measures ANOVA using linear mixed models approach.

Alternate Approaches: Diagnostics of the residuals will be performed to test the assumptions of the analysis. If the assumptions are found to be inadequate, alternative methods of analysis (e.g. ordinal logistic regression or Poisson regression) will be considered.

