The primary dependent variables in all three analyses will be intervention group (ketamine or placebo), time (number of days), and the interaction between the two. Main hypothesis of interest will be the interaction and the post-hoc comparison at the one month after the first intervention. We anticipate the study population to include participants that are currently on antidepressants as well as those that are not. We considered stratifying randomization by this variable, however since the proporption of participants on antidepressants at baseline is expected to be small, this will be considered as an independent variable in the statistical analysis. To account for within subject correlations, several structures, such as spatial autocorrelation (to accommodate unequal time points), and AR(1) symmetry, will be examined. Diagnostics will be considered. An arcsine square root transformation may be considered to stabilize variance of the proportions. In all of the analyses, covariates will be considered to examine mediations. In a secondary analysis based on the spaghetti plots, we will consider linear and non-linear models of outcomes as a function of time. Specifically, over the 8-week follow-up period, we will examine if there exists a threshold point in time where the effect of ketamine plateaus. To achieve this, treating the joint-point as unknown, we will fit segmented regression models using non-linear mixed models.

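### The 14.4-point MADRS detectable difference is labelled as a one-month effect, but its stated inputs fit a seven-visit average, which is not the contrast the plan tests

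*Combined protocol and SAP*

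**What the plan says.** Section 12.3 says the study is powered for the MADRS effect at the end of one month and refers to Hypothesis 1. At 80% power, 15 per arm "will allow us to detect a minimum difference in MADRS scores of 14.4 at one month", "in a study design with 7 repeated measurements having a AR(1) correlation of 0.9, and a standard deviation of 15.8", at a significance level of 0.050. With dropout leaving 12 per arm, the detectable differences become "a minimum MADRS score difference of 16.1 and a 26% difference between groups". The section does not name the formula, the sidedness, or whether 15.8 is the SD of a score or of a change. It assumes a mean baseline MADRS of 34 and adds: "The minimum difference in MADRS of 14.4 is anticipated to be approximately 50% of the baseline measurements".

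The tested effect is described elsewhere:

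- Section 12.2, Hypothesis 1: "Ketamine will result in significantly greater reduction in depression symptoms as compared to placebo at one-month".
- Section 12.2, on the models: "Main hypothesis of interest will be the interaction and the post-hoc comparison at the one month after the first intervention".
- Section 4.2, on the MADRS outcome: "which will be calculated as a change from baseline to 4-week followup".
- Section 12.1, on placebo participants who may go on to ketamine: "who complete Study Wk4 (at which time main outcomes are assessed".

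Table 2 (section 10.3) schedules the MADRS at baseline, Tx2, Tx4, Tx6, Tx8 and the 1-, 2- and 4-week follow-ups, eight occasions in all.

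**The concern.** A detectable difference has meaning only for the contrast it was computed for. The text ties 14.4 to one month, but seven repeated measures and a correlation of 0.9 are the inputs of a calculation that averages over visits. Neither section 4.2 nor section 12.2 makes a visit average the tested effect.

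The schedule sharpens the mismatch. Only five MADRS measurements, counting baseline, fall by Tx8. A seventh is reached at Week 6 if baseline is counted, and at Week 8 if it is not. Section 10.1 lets placebo participants start ketamine in Study Wk 5, so an average reaching that far is not a one-month comparison of ketamine with placebo.

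Readers will judge the Hypothesis 1 result against 14.4 points at 80% power. If that figure was derived for another quantity, they do not know what power the tested comparison has.

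**Working it through.** **Inputs from section 12.3:** n = 15 or 12 per arm, SD 15.8, seven measures, AR(1) correlation 0.9, significance level 0.05, power 80%. **Assumptions:** two-sided test, normal (z) approximation, so the multiplier is 1.9600 + 0.8416 = 2.8016.

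**Step 1. Reproduce the printed figures.** The variance of a seven-visit average, relative to a single visit, is the mean of the 7 × 7 AR(1) matrix: 39.093 / 49 = 0.7978. The detectable difference is 2.8016 × 15.8 × √(0.7978 × 2/n):

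- n = 15: 14.44 (printed 14.4)
- n = 12: 16.14 (printed 16.1)

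The count of seven matters: averages over 5, 6 or 8 visits give 14.92, 14.67 or 14.21 at n = 15. The 16.1 is no second confirmation, because 14.4 × √(15/12) = 16.1 under any formula of this type.

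**Step 2. Try the alternatives.**

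- Single visit, two-sided: 2.8016 × 15.8 × √(2/n) = 16.16 and 18.07. Does not match.
- Linear group-by-time slope over seven equally spaced visits, first to last (variance factor 0.937): 15.65 and 17.49. Does not match.
- Single visit, one-sided: 2.4865 × 15.8 × √(2/n) = 14.35 and 16.04. With rounded table values (1.65 + 0.84 = 2.49) it is 14.37 and 16.06, which would print as 14.4 and 16.1. It gives the seven measures and the correlation no role.

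The Hypothesis 2 figures (22% and 26%, SD 25%) do not settle it. Before the arcsine step, which is not described, the seven-visit average gives 22.84 and 25.54, and the one-sided single visit 22.70 and 25.38.

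**Step 3. Power for 14.4 points at the tested time.** Take 15.8 as the SD at every visit and one AR(1) step per MADRS visit in Table 2. From baseline, Tx8 (Wk 4) is four steps, so ρ = 0.9⁴ = 0.656. The 1-week follow-up (Wk 5) is five steps, so ρ = 0.9⁵ = 0.590. The SD is 15.8 × √(2(1 − ρ)) for change from baseline and 15.8 × √(1 − ρ²) with baseline adjustment. Power with 15 per arm is Φ(14.4 / (SD × √(2/15)) − 1.96).

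| Contrast | SD | Detectable at 15 / 12 per arm | Power at 14.4, 15 per arm |
|---|---|---|---|
| Single visit, unadjusted | 15.80 | 16.16 / 18.07 | 70% |
| Change from baseline, Wk 4 | 13.10 | 13.40 / 14.99 | 85% |
| Change from baseline, 1-week follow-up | 14.30 | 14.63 / 16.35 | 79% |
| Baseline-adjusted, Wk 4 | 11.92 | 12.20 / 13.64 | 91% |
| Baseline-adjusted, 1-week follow-up | 12.75 | 13.04 / 14.58 | 87% |

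With the t distribution the powers are 67%, 83%, 76%, 89% and 85%. If 15.8 is already the SD of a change, the 70% row applies to change from baseline.

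**Step 4. The baseline percentage.** 14.4 / 34 = 42.4%. Half of 34 would be 17.

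**The case against.** The strongest reply is that section 12.3 names no formula, so the seven-visit average is a deduction. A one-sided test at the one-month visit, the contrast the text names, comes within rounding. This stands in part: that reading cannot be excluded. It is the weaker one, because it leaves two stated inputs unused and no section says the test is one-sided. If it was the method, section 12.3 would still need to state the sidedness and remove the unused inputs.

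A second reply is that the arithmetic is right for a visit average and that nothing in the trial depends on it. The first half is true; apart from the 50% remark, the fault lies in the label. The second half is largely true. Sections 4.1 and 12.1 make feasibility primary, the efficacy aims in section 1.4 are preliminary, and 15 per arm is presented as a recruitment estimate. That limits the severity but leaves the power claim for Hypothesis 1 without a stated basis.

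A reader might infer from the 70% that the trial is underpowered for Hypothesis 1. The documents do not support that. The outcome is a change from baseline within a repeated-measures model, and under the stated correlation most versions of that contrast reach or exceed 80%. The opposite inference, that power is safely above 80%, is not supported either. It depends on choosing Wk 4. The first treatment is in Study Wk 1, so one month after it falls nearer the 1-week follow-up, where change-score power is 79%.

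**Conclusion.** The concern holds as a mismatch between label and calculation. From the stated inputs with a two-sided test, 14.4 and 16.1 are reproduced as differences in a seven-visit average, while the plan tests the interaction and the one-month comparison. The source of the figures is inferred, not proven.

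For the tested contrast, power at 14.4 points with 15 per arm runs from 70% to 91% (two-sided z), depending on the visit, on what 15.8 measures and on the use of baseline. The printed 80% may be too high or too low, and no definite shortfall is shown. These values rest on equal SDs across visits and one AR(1) step per visit. The entry requirement of a MADRS of at least 20 may make the baseline SD smaller.

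The statement that 14.4 is about half of baseline is wrong on the plan's own figure; it is 42%. Severity is minor.

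**What to change.** 1. Name one time point for Hypothesis 1. Reconcile Study Wk 4 (section 12.1), one month after the first intervention (section 12.2) and the 4-week follow-up (section 4.2), which could also be read as the follow-up visit in Study Wk 8.
2. Name the contrast: the between-group MADRS difference at that time from the mixed model, with baseline MADRS, which is already collected, as a pre-specified covariate. If the change score is kept instead, say so.
3. Restate the detectable difference for that contrast at 15 and 12 per arm, giving the sidedness, the type of SD and the assumed baseline correlation with its source. As a guide (two-sided z, 15.8 as a single-visit SD): 16.2 and 18.1 without adjustment. With baseline adjustment at an assumed correlation of 0.5, the SD is 15.8 × √0.75 = 13.68, which gives 14.0 and 15.7.
4. Correct the statement that 14.4 is about 50% of baseline to 42%.

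Keeping 14.4 and merely relabelling it as a seven-visit average would not be enough. The tested contrast would still have no power figure, and seven measurements run past the point at which placebo participants may start ketamine.

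The cost is wording in sections 4.2, 12.1, 12.2 and 12.3 and a short recalculation. Sample size, visits and data collected do not change.

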
12.4 Data Confidentiality Procedures

We will take rigorous precautions to maintain confidentiality for all participants, using procedures that the PI and her mentors have successfully employed in similar previous, as well as ongoing related studies. All study data related to mental health outcomes (i.e., the participant responses to questionnaires) and demographics will not have any unique identifying data attached. There will be only one master list of participants (not linked to participant responses). This list will be kept locked separate from other data and will be available only to the PI, her mentors, and approved study personnel. All data will be confidentially stored (i.e., in locked files or on encrypted servers) so as to protect the confidentiality of participant information. Access to research records (paper and computerized) will be restricted to the project staff, and to sponsor audit personnel and MUSC IRB auditors when indicated. All study personnel have completed (or will complete upon hiring) a certified program of instruction in the protection of human subjects in research, such as the University of Miami CITI course. These courses in the responsible conduct of research and the protection of human subjects will be completed on an annual basis, in compliance with MUSC regulations.

12.5 Data Quality Control Procedures

Data quality will be monitored by random inspection of the completed forms by the study team and any irregularities or problems detected will be discussed with the PI. At its discretion, the Sponsor or its designee may conduct a quality assurance audit of this study. Auditing procedures of the Sponsor and/or its designee will be followed in order to comply with GCP guidelines and ensure acceptability of the study data for registration purposes. If such an audit occurs, the Investigator will give the auditor direct access to all relevant documents, and will allocate his/her time and the time of his/her staff to the auditor as may be required to discuss findings and any relevant issues.

12.6 Study Documentation and Data Handling

PROTOCOL TITLE: Ketamine for the Treatment of Opioid Use and Depression Version Date: December 20, 2021

Any clinical study event that is judged to be an AE will be recorded on the AE form during the course of the study. The PI and/or trained Research Assistant will ensure this information is captured during every study visit. Whenever a study participant has reported an AE, the study coordinator will discuss the event immediately with the PI (if possible while the study participant is there) who will evaluate the event. If the AE is not serious, the information will be recorded, managed medically as appropriate, and the event will be followed until resolution. SAEs will also be recorded on the AE Form, managed medically as appropriate, and the event is followed until resolution. In addition, the PI will review all completed AE forms for determination of SAE that require reports to the Sponsor. The PI will inform the Sponsor immediately of knowledge of a SAE. All information available on the event (hospital records, lab tests, discharge summaries, etc.) will be forwarded to the Sponsor so they can determine whether the SAE is unexpected or associated and the reporting outcome of the SAE. As additional information becomes available on the SAE, it will be forwarded to the Sponsor. All SAE reports will be sent to the MUSC IRB within 24 hours of learning of event occurrence.

AEs/SAEs will be documented and reported as per IRB requirements. Research staff will identify AEs and obtain all available information to assess severity, seriousness, study relatedness, expectedness, outcome and the need for change or discontinuation in the study intervention. Adverse events will be documented on AE Logs and additional relevant AE information, if available, will be documented in a progress note in the research record as appropriate to allow monitoring and evaluating of the AE. If the AE meets the definition for Serious, appropriate SAE protocol specific reporting forms will be completed and disseminated to the appropriate persons and within the designated timeframes as indicated above. For each AE/SAE recorded, the research staff will follow the AE/SAE until resolution, stabilization or until the participant is no longer in the study. When a reportable SAE is identified, the research assistant will initiate an SAE form, and the following individuals will be notified within 24 hours of the site's initial notification of the SAE:

1. The PI ([name]) will provide oversight, consultation, assessment and documentation as appropriate of the SAE.

2. The research staff will notify the MUSC IRB, and complete the AE report form in conjunction with the PI. Both committees meet monthly. Communication with the MUSC IRB is through email, memos, official IRB forms, and online reporting.

3. The data safety monitoring board members.

If complete information is not available when the initial 24-hour SAE report is disseminated, followup information will be gathered to enable a complete assessment and outcome of the event. This information may include hospital discharge records, autopsy reports, clinic records, etc. The research staff will attach copies of source documents to the SAE report for the PI and for forwarding to the sponsor as appropriate. All deaths that occur during the study or 30 days post termination from the study are required to be reported as adverse events even if they are expected or unrelated. Other adverse events are reportable to the MUSC IRB if the AE is unexpected AND related or possibly related AND serious or more prevalent than expected. All three criteria must be met for an AE to be reported to the MUSC IRB. The IRB definition of unexpected is that the AE is not identified in nature, severity or frequency in the current protocol, informed consent, investigator brochure or with other current risk information. The definition of related is that there is a reasonable possibility that the adverse event may have been caused by the drug, device or intervention.

12.7 Privacy Protection and Confidentiality Assurances

While absolute confidentiality cannot be guaranteed, every possible effort will be made to protect the privacy of study participants, and all of the investigators have an excellent history of maintaining patient privacy and data security. Participants will be provided with a written informed consent document which specifies the risks and confidentiality protections and limits of study procedures. Subject names will remain confidential and all study data related to outcomes (i.e., the participant responses to questionnaires) and demographics will not have any unique identifying data attached in any way. There will be only one master list of participants (again, not linked to any participant responses) which will be

kept locked separate from all data and will be available only to the PI, Co-Is and approved study personnel. All data will be stored in a confidential manner (i.e., in locked files or on encrypted computers) so as to protect the confidentiality of participant information. Access to research records (paper and computerized) will be restricted to the project staff. Access to de-identified study data will be limited to named project investigators, sponsor audit personnel, and MUSC IRB auditors.

